#### 6.12.3.2 Oxygen Use

Oxygen use will be summarized by treatment group as shift (decrease, no change, increase) from baseline (last oxygen dose prior to the date of treatment start) at study days 3, 9, 15, 22 and 29. This information will be derived from concomitant medication data for oxygen.

# 6.12.4 Multiplicity

All secondary endpoints and the supportive analyses will be considered as descriptive evidence of efficacy and will be analyzed without any procedures to account for multiple comparisons.

# **6.13 Pharmacokinetic Analyses**

The pharmacokinetics of VERU-111 will be assessed on Day 15. Plasma samples for pharmacokinetic assessment will be taken at baseline (prior to dosing on Day 15) and at 4 hours (±2 hours), 12 hours (±2 hours) after dosing on Day 15, and at 24 hours (±2 hours) after dosing on Day 15 (prior to dosing on Day 16).

The following parameters will be estimated through standard methodology with this limited sampling schedule:

• AUC0-t Area Under Concentration Curve from time 0 to time t.

• Cmax Maximum Concentration

•  $T_{max}$  Time to  $C_{max}$ 

• kel Elimination Rate Constant

QMD Ref: Worldwide-TMP-ST-005-7.0 Effective: 12Aug2019	Governing QMD: Worldwide-SOP-ST-001	
Confidentiality Statement		
This document is the property of Worldwide Clinical Trials Inc. and may not be duplicated, copied, altered or removed from company without		
prior approval from Worldwide Quality Assurance or in compliance with Worldwide Standard Operating Procedures.		

Worldwide Clinical Trials Controlled Quality Management Document		
WORLDWIDE CLINICAL TRIALS	Sponsor:	Veru Inc.
	Protocol Number:	V0211901
STATISTICAL ANALYSIS PLAN. PHASE 2-3-4		

Cl/F Clearance
T1/2 Half-Life

• Vd/F Volume of Distribution

The limited sampling schedule is used due to limitations on study personnel entering the subject's room during the day. If the sample is missed due to restrictions in entering the room, then this sample will be listed as missing.

PK concentrations will be summarized using descriptive statistics (n, mean, standard deviation, CV(%), geometric mean, median, minimum and maximum) for absolute values by treatment group and visit. Mean plots by treatment and individual subject curves will be displayed on linear and semi-logarithmic scale (time on linear scale, concentration on logarithmic scale) for concentration data.

PK parameters will be summarized using descriptive statistics (n, mean, standard deviation, median, minimum and maximum) for absolute values by treatment group.

All PK concentration and PK parameter data will be listed.

# **6.14 Pharmacodynamic Analyses**

Not applicable.

# **6.15 Safety Analyses**

The safety analyses will be presented by the treatment received for the ITT Population.

#### **6.15.1** Adverse Events

A treatment emergent adverse event (TEAE) is defined as:

- Any AE that has an onset on or after the first dose of study drug and before last dose of study drug + 7 days.
- Any pre-existing AE that has worsened in severity on or after the first dose of study drug and before the last dose of study drug + 7 days.

A treatment-related AE is defined as an AE with causality collected as 'POSSIBLY RELATED', 'PROBABLY RELATED' or 'RELATED' in the CRF. If an AE has missing relationship it is assumed to be 'RELATED' to the study drug for analysis purposes.

QMD Ref: Worldwide-TMP-ST-005-7.0 Effective: 12Aug2019	Governing QMD: Worldwide-SOP-ST-001
Confidentiality Statement	

Worldwide Clinical Trials Controlled Quality Management Document		
WORLDWIDE CLINICAL TRIALS	Sponsor:	Veru Inc.
	Protocol Number:	V0211901
STATISTICAL ANALYSIS PLAN. PHASE 2-3-4		

If an AE has missing standard toxicity grade it is assumed to be 'GRADE 3 (SEVERE)' for analysis purposes.

AEs will be summarized according to the MedDRA (version 23.0 updated) system organ class and preferred term.

The following tables will be presented for AEs:

- Overall incidence and the number of events in the following categories:
  - o TEAEs
  - Treatment-Related TEAEs
  - Serious TEAEs
  - Treatment-Related Serious TEAEs
- For the above AE categories tables including incidence and number of events will be presented by system organ class and preferred term
- TEAEs by system organ class, preferred term and maximum toxicity grade (incidence, no event counts)
- TEAEs by system organ class, preferred term and strongest relationship grade (incidence, no event counts)
- Listing of Deaths (presented in the Table section of the appendices)
- Listing of Serious TEAEs (presented in the Table section of the appendices).

In counting the number of AEs reported, a continuous event (i.e. reported more than once and which did not cease), will be counted only once; non-continuous AE reported several times by the same subject will be counted as multiple events.

All AEs will be listed.

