Design:	This study is a multicenter, randomized, placebo-control, efficacy and safety study of VERU-111 for the treatment of COVID-19. Subjects will receive either 18 mg of VERU-111 or matching placebo orally or through nasogastric tube daily for up to 21 days or until the subject is discharged from the hospital, whichever comes first.
	The primary efficacy endpoint of the study will be the proportion of subjects that are alive without respiratory failure at Day 29. Respiratory failure is defined as endotracheal intubation and mechanical ventilation, extracorporeal membrane oxygenation, high-flow nasal cannula oxygen delivery, noninvasive positive pressure ventilation, clinical diagnosis of respiratory failure with initiation of none of these measures only when clinical decision making is driven solely by resource limitation.
	The total study duration for a subject from screening to follow up visit is planned to be 62 days.
	An evaluation of the effect of VERU-111 on SARS-CoV-2 (COVID-19) compared to the placebo control will be evaluated after the last subject has completed Day 22. This will allow for the decision to move to Phase 3 more quickly if the Phase 2 portion of the study shows a clinically relevant difference in the proportion of subjects that are alive without respiratory failure at Day 22 in the VERU-111 treated groups compared to the Placebo treatment group and VERU-111 is well tolerated in the study.
	Due to the unexpectedly slow recruitment into this study, Veru is conducting an interim analysis after the first 24 subjects have completed Day 15 or have discontinued from the study.
Subjects:	Approximately, 40 subjects are planned to be randomized at a 1:1 ratio into two treatment arms (20 subjects in the VERU-111 treated group and 20 subjects in the Placebo treated group).
	The subjects with documented evidence of COVID-19 infection will be enrolled.
Treatments:	Subjects in the VERU-111 treatment groups will receive standard of care, plus oral daily VERU-111 18 mg for 21 days or until released from hospital.
	Subjects in the Placebo treatment group will receive standard of care, plus a placebo capsule for 21 days or until released from hospital.

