8.11.4 Initial Reports

SAEs will be collected from the time of first study drug administration through 60 days after first study drug administration. SAEs and events of clinical interest must be reported to the Sponsor (or designee) within 24 hours of the knowledge of the occurrence.

In the event an SAE is observed or reported, the SAE report will be completed as thoroughly as possible including all available details about the event and the signature of the Investigator. If the Investigator does not have all information about an SAE, the Investigator will not wait to receive additional information before notifying the Sponsor of the event and completing the form. The form will be updated when additional information is received.

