9.7 Safety Analysis

The frequency of adverse events (AEs) will be tabulated by MedDRA term and system organ class. The incidence of AEs and the maximum intensity and frequency of AEs will be summarized. A new onset AE is defined as an AE that was not present prior to treatment with study medication but appeared following treatment or was present at treatment initiation but worsened during treatment. An AE that was present at treatment initiation but resolved and then reappeared while the subject was on treatment is a new-onset AE (regardless of the intensity of the AE when the treatment was initiated).

All laboratory results, vital sign measurements, and other safety variables will be summarized using appropriate descriptive statistics. Changes from baseline will be computed and will be summarized using appropriate descriptive statistics.

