# **6.2.2 Duration / Study Day / Time**

Study day will be calculated as the number of days from first dose of study drug.

- date of event date of first dose of study drug + 1, for events on or after first dose
- date of event date of first dose of study drug, for events before first dose

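### All by-arm adverse event tables stop at last dose + 7 days, so non-fatal events from then to Day 60 reach only the subject listings, and the length of the counted period depends on discharge

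*SAP*

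**What the plan says.** SAP 6.15.1 defines the first type of treatment-emergent event (TEAE) as one that begins no earlier than the first dose and "before last dose of study drug + 7 days". The second type, a pre-existing event that worsens, has the same cut-off. The AE tables planned in that section, and numbered 14.3.1.1.1 to 14.3.1.3.2 in SAP Section 11, are all TEAE tables: overall, related, serious, related serious, by grade and by relationship. The serious-event listing (14.3.2.2) is also limited to TEAEs. The deaths listing (14.3.2.1) and the listing of all AEs (16.2.7.1) are not.

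The date of last dose is set by the protocol's dosing rule: treatment is given for "up to 21 days or until the subject is discharged from the hospital, whichever comes first" (Protocol 2.0, Design).

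The protocol collects safety data for longer. Protocol 5.2 continues safety assessments to Day 60, and Protocol 2.0 (Procedures) and 8.8 schedule AE assessments at Days 45 and 60. Protocol 8.11.4 states: "SAEs will be collected from the time of first study drug administration through 60 days after first study drug administration".

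The analysis definition in Protocol 9.7 begins "A new onset AE is defined as an AE that was not present prior to treatment with study medication but appeared following treatment", with no limit on how long after dosing a new event may appear. SAP Section 9 lists five changes from the protocol's analysis (covariates, a dropped secondary endpoint, the interim analysis, the ITT definition and the EE population). The TEAE window is not among them.

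**The concern.** Two separate things follow from this.

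- **Coverage.** More than half of the calendar period over which safety data are collected cannot contribute to any by-arm incidence table, even for a subject who completes all 21 doses. A late non-fatal SAE would be in no by-arm table and not in the serious-event listing placed with the tables.
- **Comparability.** The window is anchored to the last dose, which usually means discharge. Discharge and days in hospital are themselves secondary efficacy endpoints. If the arms differ in discharge times, they are counted over different lengths of time, and crude incidence would differ even with no difference in risk.

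Safety and tolerability is a stated objective. With about 20 subjects per arm, one subject is 5 percentage points, so a few late events in one arm could alter how the safety profile reads.

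**Working it through.** **Inputs.** First dose is study Day 1 (SAP 6.2.2). Onset must fall before last dose + 7 days (SAP 6.15.1). The last planned dose is on Day 21 or at discharge (Protocol 2.0; Appendix B, footnote b). Follow-up runs to Day 60 (Protocol 5.2), and screening takes 2 days (Protocol 8.1). The documents give no AE rates and no discharge times, so those below are assumptions.

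**The plan's own figure.** 2 screening days + 60 study days = 62 days, which matches the stated duration per subject.

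**Coverage.** If the last dose is on Day L, the last qualifying onset day is L + 7 - 1 = L + 6. Days outside the window = 60 - (L + 6).

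| Last dose | Window closes | Days outside | Share of Days 1-60 |
|---|---|---|---|
| Day 21 | Day 27 | 33 | 33/60 = 55% |
| Day 14 | Day 20 | 40 | 40/60 = 67% |
| Day 7 | Day 13 | 47 | 47/60 = 78% |
| Day 5 | Day 11 | 49 | 49/60 = 82% |

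The first row is the smallest loss possible under planned dosing. The rule uses onset date, so an event that began inside the window but was recorded at a later visit still counts.

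**Comparability.** Assume the same constant hazard h per day in both arms. Incidence over a window of W days is 1 - exp(-hW). Last dose on Day 7, 8 or 14 gives W = 13, 14 or 20.

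| h per day | W = 13 | W = 14 | W = 20 | Day 7 v 8 | Day 7 v 14 |
|---|---|---|---|---|---|
| 0.01 | 12.2% | 13.1% | 18.1% | 0.9 points | 5.9 points |
| 0.02 | 22.9% | 24.4% | 33.0% | 1.5 points | 10.1 points |
| 0.03 | 32.3% | 34.3% | 45.1% | 2.0 points | 12.8 points |

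The expected ratio of event counts does not depend on h: 13/14 = 0.93 for the one-day gap and 13/20 = 0.65 for the seven-day gap. With 20 per arm, the one-day gap is worth less than one subject (0.02 x 20 = 0.4) and the seven-day gap about one to three (0.059 x 20 = 1.2; 0.128 x 20 = 2.6).

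**After the fix.** With a window fixed at Days 1-60, every subject alive and in follow-up contributes 60 days whatever the discharge date. The expected ratio under equal hazards is then 60/60 = 1.00.

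**The case against.** A last-dose-plus-lag window is a legitimate on-treatment view, and several points against a stronger reading stand.

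- **Delayed SAEs are not hidden from comparison.** A reader might infer that they are never compared between arms. All AEs are listed, listings are sorted by treatment group (SAP 6.3), and the AE listing goes to the DSMB (LS3), which reviews all SAEs unblinded (Protocol 9.7.1). The deaths listing is unrestricted, and mortality is modelled by arm at Days 15, 22 and 29 (SAP 6.12.2.5). WHO-scale treatment differences are presented to Day 60. The gap is confined to incidence tables for late non-fatal events.
- **The departure from Protocol 9.7 is partial.** Only the limb on newly appearing events is open-ended. The limbs on worsening and recurrence are tied to being on treatment, and for worsening the SAP is wider by 7 days.
- **Calendar days overstate the loss of scheduled assessments.** AE assessments fall on Days 1-21, 22, 29, 45 and 60. For a full course, 22 of 25 (88%) are inside the window. With a last dose on Day 5 it is 11 of 25 (44%), if daily assessment continues after discharge. SAEs are reportable within 24 hours of becoming known, so visit counts say little about them.
- **The arm effect is conditional.** A reader might infer that VERU-111 would look safer merely through earlier discharge. The documents do not show which arm leaves earlier or by how much, and death or stopping for toxicity also moves the last dose. A constant hazard from acute illness through recovery is itself doubtful.

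What survives is the missing by-arm tabulation and the dependence of the window on an outcome.

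**Conclusion.** The point holds in limited form. The closing day (Day 27 at the latest) and the excluded share (55% of Days 1-60 at minimum, 82% for a last dose on Day 5) follow from the documents with no assumption beyond planned dosing. The possible distortion between arms does rest on assumptions: about 1-2 points for a one-day gap in last dose and 6-13 points for a seven-day gap, under equal constant hazards of 0.01-0.03 per day. It is zero if discharge times match and could favour either arm. No single figure should be quoted as the expected bias. The data are not lost, but their by-arm summary is not planned, and Section 9 does not disclose the narrowing for newly appearing events. That deserves correction even in an unpowered proof-of-concept study, because safety is an objective and the data are already being collected.

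**What to change.** 1. Add by-arm AE and SAE incidence tables covering all events from first dose to Day 60, using the existing shells. Exposure-adjusted rates are a useful option.
2. Keep the last-dose + 7 days tables alongside as the on-treatment view. Which set is called primary is a matter of preference; the documents do not require the Day 60 set to take that place.
3. Do not restrict the serious-event listing (14.3.2.2) to TEAEs.
4. Record the TEAE window in SAP Section 9, noting that it narrows Protocol 9.7 for newly appearing events and widens it for worsening ones.

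The cost is a few more tables from data already in hand. The limitation to state with them is that post-discharge events are ascertained less often, and the Day 45 and Day 60 contacts may be by telephone. A fixed window therefore equalises the counting period but not the intensity of observation, and early deaths still shorten follow-up.

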# 6.15.2 Laboratory Data

Laboratory data will be collected in local labs and the units need to be made consistent before presenting in summary tables.

Descriptive statistics of the observed values and change from baseline (continuous data) will be presented by treatment group and visit for each chemistry, hematology and urinalysis parameter.

Each measurement (continuous data) will be classed as below, within, or above normal range, based on ranges supplied by the laboratory used. Shift tables in relation to the normal range from baseline to each timepoint will be presented.

QMD Ref: Worldwide-TMP-ST-005-7.0 Effective: 12Aug2019	Governing QMD: Worldwide-SOP-ST-001	
Confidentiality Statement		
This document is the property of Worldwide Clinical Trials Inc. and may not be duplicated, copied, altered or removed from company without		
prior approval from Worldwide Quality Assurance or in compliance with Worldwide Standard Operating Procedures.		

Worldwide Clinical Trials Controlled Quality Management Document		
WORLDWIDE CLINICAL TRIALS	Sponsor:	Veru Inc.
	Protocol Number:	V0211901
STATISTICAL ANALYSIS PLAN. PHASE 2-3-4		

A listing of any clinically significant laboratory measurements recorded throughout the study will be presented in tables section.

All laboratory data will be listed.

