6.2.2 Exclusion Criteria

Any of the following conditions are cause for exclusion from the study:

- 1. Known hypersensitivity or allergy to colchicine
- 2. Participation in any other clinical trial of an experimental treatment for COVID-19. Convalescent plasma and remdesivir are allowed in this study.

- 3. Concurrent treatment with other experimental agents with actual or possible direct acting antiviral activity against COVID-19 is prohibited < 24 hours prior to study drug dosing (except standard of care). Remdesivir and convalescent plasma are allowed in the study.
- Requiring ventilation + additional organ support pressors, RRT, ECMO (WHO Ordinal Scale for Clinical Improvement – Score of 7) and patients requiring ventilation with a WHO Ordinal Scale for Clinical Improvement – Score of 6 for >5 days at screening.
 - Patients on ventilation with a WHO Ordinal Scale for Clinical Improvement Score of 5 (non-invasive ventilation or high-flow oxygen) are allowed into the study.
 - Patients on ventilation with a WHO Ordinal Scale for Clinical Improvement Score of 6 (intubation and mechanical ventilation) for less than five (5) days are allowed into the study.
- 5. Alanine Aminotransferase (ALT) or aspartate aminotransferase (AST) >2 X upper limit of normal (ULN)
- 6. Total bilirubin > ULN
- 7. Creatinine clearance < 60 mL/min
- 8. Documented medical history of liver disease, including but not limited to, prior diagnosis of hepatitis of any etiology, cirrhosis, portal hypertension, or confirmed or suspected esophageal varices
- 9. Moderate to severe renal impairment
- 10. Hepatic impairment
- 11. History of hepatitis
- 12. Any comorbid disease or condition (medical or surgical) which might compromise the hematologic, cardiovascular, endocrine, pulmonary, renal, gastrointestinal, hepatic, or central nervous system; or other conditions that may interfere with the absorption, distribution, metabolism or excretion of study drug, or would place the subject at increased risk
- 13. Participants must agree to refrain from prolonged exposure to the sun or agree to use at least SPF 50 on all exposed skin and protective clothing during prolonged sun exposure throughout participation in this study and/or treatment with VERU-111.

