8.9 Subject Stopping Rules

If, in the opinion of the investigator, the participation in the study is or is becoming detrimental to the well-being of a particular subject, this issue should be discussed with the Medical Monitor for this study and dosing may be discontinued.

Subjects that experience a Grade 4 or greater toxicity according to the Common Terminology Criteria for Adverse Events (CTCAE) version 4 (https://evs.nci.nih.gov/ftp1/CTCAE/CTCAE 4.03 2010-06-14 QuickReference 5x7.pdf)

that is deemed to be possible, probably or definitely related to study drug will be discontinued from the study. Prior to discontinuation from the study, the grading of the event and causal relationship should be discussed with the Medical Monitor for the study.

Subjects will be discontinued from dosing if AST or ALT levels are >5 times the upper limit of normal, or if AST or ALT levels are >3 times the upper limit of normal along with a total bilirubin elevation of >2 times the upper limit of normal.

Subjects will be discontinued from dosing if Grade 3 diarrhea is observed.

Subjects will be discontinued from dosing if Grade 3 neutropenia is observed.

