8.11 Adverse Events

An adverse event (AE) is any unfavorable or unintended change in body structure (signs) or body function (symptoms), abnormal laboratory result that is associated with symptoms or requires treatment or worsening of a pre-existing condition. This includes all such events regardless of the presumed relationship between the event and the study medication(s).

Any AE that occurs after the informed consent is signed but prior to dosing on Day 1 will be captured as part of the medical history and will be documented on the appropriate eCRF. This would include AEs resulting from concurrent illnesses, reactions to concomitant medications or progressive disease states. These AEs will be captured as part of the medical history.

Each subject will be assessed for the development of any adverse events. Adverse events should be assessed at each visit to the clinic. This information should be obtained in the form of non-leading questions (e.g., "How are you feeling?") and from signs and symptoms detected during each examination, observations of the study personnel or spontaneous reports from the subjects.

Any AEs such as complaints, signs, or symptoms that occur during the course of the study or designated follow-up periods will be recorded on the subject's case report form (eCRF). This would include AEs resulting from concurrent illnesses, reactions to concomitant medications, or progressive disease states.

Whenever possible, the AE will be described on the case report form using standard medical terminology consistent with Common Terminology Criteria for Adverse Events (CTCAE) version 4 in order to avoid the use of vague, ambiguous or colloquial expressions. The investigator will evaluate all adverse events as to their intensity, relation to test medication, outcome and action taken.

Each AE will be evaluated for duration, intensity, and relationship to (or association with) the study treatment (or other causes). Additionally, the actions taken (e.g., reduction of dosage, discontinuation of study medication, administration of treatment, etc.) and the resulting outcome of the AE will be indicated on the case report form.

Any subject who is withdrawn from the study due to an adverse event will be followed until the outcome of the event is determined, and the investigator will prepare a written summary of the event and document the available follow-up information on the case report form.

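### Three laboratory-defined dose-stopping criteria in protocol 8.9 (two liver, one neutrophil) have no prespecified count by arm

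*SAP*

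**What the plan says.** SAP 6.15.2 plans four kinds of laboratory output.

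- Summary statistics: "Descriptive statistics of the observed values and change from baseline (continuous data) will be presented by treatment group and visit". Under SAP 6.3 these include the minimum and maximum.
- Shift tables from baseline to each timepoint in three classes: "Each measurement (continuous data) will be classed as below, within, or above normal range, based on ranges supplied by the laboratory used".
- A listing: "A listing of any clinically significant laboratory measurements recorded throughout the study will be presented in tables section".
- A full listing of all laboratory data.

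SAP 6.2.9 keeps repeat and unscheduled post-baseline results out of the tables; they are only listed.

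Protocol 8.9 has five objective stopping criteria.

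- A related severe toxicity: "Subjects that experience a Grade 4 or greater toxicity according to the Common Terminology Criteria for Adverse Events (CTCAE) version 4".
- A transaminase limit: "Subjects will be discontinued from dosing if AST or ALT levels are >5 times the upper limit of normal".
- ALT or AST above 3 times ULN together with total bilirubin above 2 times ULN.
- Grade 3 diarrhea.
- Grade 3 neutropenia.

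Protocol 8.11 limits which laboratory results are AEs. The definition covers an "abnormal laboratory result that is associated with symptoms or requires treatment or worsening of a pre-existing condition". The exclusion criteria (protocol 6.2.2) allow ALT and AST up to 2 times ULN at entry. In the protocol summary, the move to Phase 3 depends on efficacy and on whether "VERU-111 is well tolerated in the study".

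**The concern.** The protocol sets its own thresholds for liver and neutrophil toxicity that ends dosing, in ULN multiples and Common Terminology Criteria for Adverse Events (CTCAE) grade. The SAP summarizes the same analytes on a scale that cannot separate values on either side of those thresholds. A reader of the planned tables could not say how many subjects in each arm met a laboratory stopping criterion, or whether dosing then stopped.

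That count bears directly on the tolerability half of the Phase 3 decision. It also bears on protocol 3.2, which describes the drug as not causing neutropenia or myelosuppression: the plan has no tabulation of graded neutrophil counts with which to check that here. A count of zero would be as useful to the sponsor as a non-zero one.

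**Working it through.** The plan states no figure to reproduce, because neither document gives a safety event rate or a power calculation. The check maps each criterion to the planned outputs.

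**Step 1. Criteria against planned tables (SAP 6.15.1, 6.15.2 and section 11)**

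| Criterion in protocol 8.9 | Basis | Planned count by arm |
|---|---|---|
| Related Grade 4 or greater toxicity | AE grade | Yes, by grade in Table 14.3.1.3.1; relatedness is in a separate table |
| ALT/AST >5x ULN | Laboratory value | None |
| ALT/AST >3x ULN with bilirubin >2x ULN | Two laboratory values | None |
| Grade 3 diarrhea | AE grade | Yes, Table 14.3.1.3.1 |
| Grade 3 neutropenia | Laboratory value | None |

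Three of the five depend on laboratory values. Tables 14.3.4 to 14.3.5 contain no display by ULN multiple, by CTCAE laboratory grade, or for the joint liver criterion.

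**Step 2. What the three-class shift shows (ALT in multiples of ULN; illustrative values)**

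| Baseline | Follow-up | Shift cell | Above 5x? |
|---|---|---|---|
| 1.5 | 6 | above to above | yes |
| 1.5 | 1.6 | above to above | no |
| 0.8 | 6 | within to above | yes |
| 0.8 | 1.1 | within to above | no |

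Each cell mixes values that meet the criterion with values that do not. A baseline of 1.5 is permitted at entry. All low neutrophil counts share one class. The joint criterion needs two analytes in one subject, so no single-parameter table can show it.

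**Step 3. Other routes to the count**

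- *AE tables.* A new, asymptomatic, untreated abnormality need not be an AE under protocol 8.11, so it may not reach the graded table.
- *Withdrawals.* SAP 6.4 tabulates early withdrawals by reason. The three laboratory criteria stop dosing rather than study participation, and the reasons in protocol 8.10 name no laboratory criterion.
- *Exposure.* SAP 6.2.7 and 6.9 give days only. Dosing also ends at hospital discharge, so short exposure does not identify a toxicity stop.
- *Unscheduled peaks.* Scheduled post-baseline draws are on Days 3, 9, 15, 22 and 29. A peak between them is listed but not tabulated. SAP 6.15.4 and 6.15.5 use the worst post-baseline record for physical examination and ECG shifts; 6.15.2 does not do so for laboratory data.

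**Step 4. What a count would tell, with the planned 20 per arm**

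Exact two-sided 95% upper limit for 0/20: 1 − 0.025^(1/20) = 16.8%.

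Chance of at least one case in an arm: 1 − (1 − p)^20. The rates p are assumptions.

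| Assumed true rate p | Chance of at least one case in 20 |
|---|---|
| 2% | 33% |
| 5% | 64% |
| 10% | 88% |
| 15% | 96% |

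**The case against.** The best defence is that the safety output is richer than the shift table. Minimum and maximum by arm and visit would expose an extreme scheduled ALT or neutrophil value. All laboratory data are listed by treatment group, so with about 40 subjects a hand count is feasible. The data safety monitoring board sees unblinded safety data every two weeks, including hematology and chemistry summaries and listings. The reason for stopping study treatment must be documented. A laboratory stop reported as an AE would be counted by preferred term and grade. The study is an unpowered proof of concept with descriptive safety analysis.

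Most of this stands and limits the point. A maximum does not count subjects. It is also in raw units pooled over local laboratories whose limits may differ. Listings permit a count but none is prespecified, and the board's outputs are the same summaries and listings.

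Four stronger readings are tempting, and the documents do not support them.

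- *None of the 8.9 toxicities is counted by arm.* Grade 3 diarrhea and Grade 4 or greater AEs are, in the maximum-grade TEAE table.
- *Asymptomatic laboratory changes are never AEs.* One that needs treatment is an AE. On one reading of protocol 8.11, so is one that worsens a pre-existing condition, which could include the 1.5 to 6 example.
- *The shift counts are wrong.* They are correct counts of normal-range shifts, but coarse.
- *The arms would look alike on laboratory safety.* The extremes by arm may well show a difference.

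**Conclusion.** The point holds for three criteria: ALT/AST above 5 times ULN, ALT/AST above 3 times ULN with bilirubin above 2 times ULN, and Grade 3 neutropenia. No planned output gives the number of subjects per arm who met them, and the AE, withdrawal and exposure tables do not reliably supply it.

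The gap is in presentation. It does not bias any planned analysis, and the data to close it are collected. Its practical size cannot be stated, because the documents give no rates for these events; the probabilities above rest on assumed rates and the planned 20 per arm. Even a complete count would be imprecise, as the 16.8% limit for 0/20 shows. The change is still worth making because tolerability is a stated condition for Phase 3. The stopping rules themselves are not in question.

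**What to change.** In SAP 6.15.2, keep the normal-range shifts and add the following.

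1. By-arm shift tables from baseline to worst post-baseline value, using scheduled and unscheduled results, with a stated exception to SAP 6.2.9. Use each local laboratory's ULN and the multiples already in the protocol: ALT/AST at ≤2, >2 to 3, >3 to 5 and >5; bilirubin at ≤1, >1 to 2 and >2. Show neutrophils by CTCAE version 4 grade.
2. One by-arm table of subjects meeting each of the three laboratory criteria while on treatment (first to last dose), and whether dosing stopped. Show values after the last dose separately.

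The separation matters because dosing ends by Day 21 or discharge, so Day 29 samples, and usually Day 22 samples, cannot have triggered a stop. Assign values by dosing date rather than visit label: the Day 22 window of ±3 days reaches back to Day 19. The documents do not fix the time of safety draws relative to dosing. A sample taken before that day's dose could itself lead to the stop and then fall after the last dose by date, so such values should be flagged.

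The cost is SAP wording and two or three descriptive tables from local values, local ranges, the differential and the dosing log. No procedure or clinical rule changes. The downside is a longer safety section and a possibly less favourable display. SAP section 6 would allow such tables to be added in the study report, but specifying them before unblinding avoids the appearance of selection.
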